Appendix 4: Contraceptive Guidance and Collection of Pregnancy Information

Female participants presenting with oligomenorrhea or amenorrhea who are aged ≤ 55 years should be considered potentially fertile and therefore should undergo pregnancy testing like all other female participants.

Definitions

Woman of Childbearing Potential (WOCBP)

A woman is considered fertile following menarche and until becoming post-menopausal unless permanently sterile (see below).

Women in the following categories are not considered WOCBP

1. Pre-menopausal female with 1 of the following:
 - documented hysterectomy
 - documented bilateral salpingectomy
 - documented bilateral oophorectomy.
2. Post-menopausal female
 - A post-menopausal state is defined as a woman over 55 years who has not had menses for 12 months without an alternative medical cause. A high FSH level in the post-menopausal range may be used to confirm a post-menopausal state in women not using hormonal contraception or hormone replacement therapy (HRT). However, in the absence of 12 months of amenorrhea, a single FSH measurement is insufficient.
 - Females on HRT and whose menopausal status is in doubt will be required to use one of the non-hormonal highly effective contraception methods if they wish to continue their HRT during the study. Otherwise, they must discontinue HRT to allow confirmation of post-menopausal status before study enrollment.

Contraception Guidance

Couples should agree not to try to become pregnant during this study. It should be noted that Chronocort treatment may result in improved fertility and so appropriate precautions against pregnancy should be taken.

Male participants

- Male participants with female partners of childbearing potential are eligible to participate if they agree to ONE of the following:
 - Are abstinent from penile-vaginal intercourse as their usual and preferred lifestyle (abstinent on a long-term and persistent basis) and agree to remain abstinent.
 - Agree to use a male condom when having penile-vaginal intercourse with a WOCBP who is not currently pregnant.

Men with a pregnant or breastfeeding partner must agree to remain abstinent from penile-vaginal intercourse or use a male condom during each episode of penile penetration

for the duration of the study. Men must also refrain from donating sperm for the duration of the study and for 7 days after the last dose of study treatment.

Female participants

Female participants of childbearing potential are eligible to participate if they agree to use a highly effective method of contraception consistently and correctly as described in the table below. The methods of contraception must remain the same throughout the study in both nature and dose. The type of contraception should have been ongoing for ≥ 90 days prior to the study and at least 7 days after the final dose. If < 90 days prior to the study, additional use of a double barrier method until 90 days is reached is required.

Contraceptive Methods

Highly Effective Methods That Are User Dependent^a
 
Failure rate of <1% per year when used consistently and correctly.

Combined (estrogen and progestogen containing) hormonal contraception associated with inhibition of ovulation^b
 
• oral• intra-vaginal• trans-dermal.

Progestogen only hormonal contraception associated with inhibition of ovulation
 
• oral• injectable.

Highly Effective Methods That Are User Independent^a

Implantable progestogen only hormonal contraception associated with inhibition of ovulation^b
 
• intra-uterine device• intra-uterine hormone-releasing system.• Bilateral tubal occlusion.

Vasectomized partner
 
A vasectomized partner is a highly effective contraception method provided that the partner is the sole male sexual partner of the WOCBP and the absence of sperm has been confirmed. If not, an additional highly effective method of contraception should be used.

Sexual abstinence
 
Sexual abstinence is considered a highly effective method only if defined as refraining from heterosexual intercourse during the entire period of risk associated with the study treatment. The reliability of sexual abstinence needs to be evaluated in relation to the duration of the study and the preferred and usual lifestyle of the participant.

Barrier methods of contraception

Condom or occlusive cap (diaphragm or cervical/vault caps) with spermicidal foam/gel/film/cream/suppository. The following should be noted:

Failure rates indicate that, when used alone, the diaphragm and condom are not highly effective forms of contraception. Therefore, the use of additional spermicides does confer additional theoretical contraceptive protection. However, spermicides alone are inefficient at preventing pregnancy when the whole ejaculate is spilled. Therefore, spermicides are not a barrier method of contraception and should not be used alone.

NOTES:

- a) Typical use failure rates may differ from those when used consistently and correctly. Use should be consistent with local regulations regarding the use of contraceptive methods for participants participating in clinical studies.
- b) Hormonal contraception may be susceptible to interaction with the study treatment, which may reduce the efficacy of the contraceptive method. In this case, 2 highly effective methods of contraception should be utilized during the treatment period and for 7 days after the last dose of study treatment.

Pregnancy testing

- WOCBP should only be included after a confirmed negative highly sensitive urine pregnancy test (or blood test if required according to usual site practices) taken at the screening visit (Visit 1).
- Additional pregnancy testing should be performed at every clinic visit from Visit 2 onwards.
- Pregnancy testing will be performed if pregnancy is suspected.

Collection of Pregnancy Information**Male participants with partners who become pregnant**

- The Investigator will attempt to collect pregnancy information on any male participant's female partner who becomes pregnant while the male participant is in this study.
- After obtaining the necessary signed informed consent from the pregnant female partner directly, the Investigator will record pregnancy information on the appropriate form and submit it to the Sponsor within 24 hours of learning of the partner's pregnancy to Pharmalex ([contact]). The female partner will also be followed up to determine the outcome of the pregnancy. Information on the status of the mother and child will be forwarded to the Sponsor. Generally, the follow-up will be no longer than 6 to 8 weeks following the estimated delivery date. Any termination of the pregnancy will be reported regardless of fetal status (presence or absence of anomalies) or indication for the procedure.

Female Participants who become pregnant

- The Investigator will collect pregnancy information on any female participant who becomes pregnant while participating in this study. Information will be recorded on the appropriate form and submitted to the Sponsor within 24 hours of learning of a participant's pregnancy to Pharmalex ([contact]). The participant will be followed up to determine the outcome of the pregnancy. The Investigator will collect follow-up information on the participant and the neonate and the information will be forwarded to the Sponsor. Generally, follow-up will not be required for longer than 6 to 8 weeks beyond the estimated delivery date. Any

termination of pregnancy will be reported, regardless of fetal status (presence or absence of anomalies) or indication for the procedure.

- While pregnancy itself is not considered to be an AE or SAE, any pregnancy complication or elective termination of a pregnancy will be reported as an AE or SAE.
- A spontaneous abortion (occurring at <22 weeks gestational age) or still birth (occurring at >22 weeks gestational age) is always considered to be an SAE and will be reported as such.
- Any post-study pregnancy-related SAE considered reasonably related to the study treatment by the Investigator will be reported to the Sponsor as described in Section 8.4.1. While the Investigator is not obligated to actively seek this information in former study participants, he/she may learn of an SAE through spontaneous reporting.
- Any female participant who becomes pregnant while participating in the study will discontinue study treatment and will be followed up as detailed above (with consent of the participant). However, participants who withdraw from the study due to pregnancy may be eligible to enter the long-term extension study (DIUR-015) at the discretion of the Investigator providing that at least 6 weeks has lapsed after the pregnancy is complete (i.e. at least 6 weeks post-partum regardless of outcome or at least 6 weeks after abortion or termination) or at least 6 weeks after they have finished lactating and are no longer breast feeding (whichever is longer).

Appendix 5: Adrenal Insufficiency Checklist

*This questionnaire should be used to determine if symptoms of **under- or over-replacement of glucocorticoids** have occurred in the preceding 4 weeks. Symptoms unrelated to CAH, but due to other causes, e.g. nausea with migraine, should be recorded on the eCRF AE page.*

Date of assessment (mm/dd/yyyy):				
Please ask subject:		Have you experienced any of the following symptoms more than once per week in the last 4 weeks?		
Symptoms	Yes	If Yes, do you believe this to be related to under or over replacement of glucocorticoid? Please state over/under.	No	Any clinically significant findings? Y/N
Sudden weight loss				
Sudden weight gain				
Lack of appetite				
Increased appetite				
Nausea				
Vomiting				
Headache				
Blurred vision				
Fatigue				
Weakness				
Dizziness				
Lightheadedness				
Syncope (sudden loss of consciousness)				
Sleeping difficulties				
Increased acne				
Other				
If yes to Other please specify:				

Version FINAL 1.0 – 01 Sept 2015

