The analysis of all 17-OHP and A4 levels will be conducted by a central laboratory and the results will be sent to an independent blinded physician, with the independent blinded physician being unaware of the participant's treatment allocation. The Investigator will also complete an adrenal insufficiency checklist at each visit which will be made available to the independent blinded physician. If at the titration visits at Weeks 4, 10, and 16 the independent blinded physician considers a dose reduction is necessary, the dose should be reduced by a total of 5 mg at each titration visit. Each treatment arm will be subject to the same titration rules throughout the study, ensuring that opportunities for optimization and control of androgens are the same in both arms and thus minimizing bias in the management of participants. At the titration visits at Weeks 4, 10, and 16, only dose reductions are permitted, unless the dose has previously been reduced, in which case it can be reverted back to the previous higher dose if needed without having to wait until the next titration point. Dose increases can only be made in an urgent situation where the Investigator believes the participant is exhibiting signs of adrenal insufficiency, and in all cases, this should be discussed with the medical monitor before a dose increase is initiated (see Section 4.2 for further details).

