of the reference range), then the dose will be adjusted down by a total of 5 mg. If one or both androgen results are above these limits, then no titration will be undertaken. Clinical symptoms of adrenal insufficiency on the adrenal insufficiency checklist should take precedence over androgen results and would inhibit titration. Only 1 of the 2 doses a participant receives (i.e. morning or afternoon/evening) should be titrated at each titration point but no dose should be reduced below 5 mg. If the androgen results indicate that both doses should be reduced, then precedence should be given to reducing the morning dose of Chronocort and the afternoon dose of IRHC. If the same situation then recurs at the next titration timepoint then the dose reduced should be alternated to avoid a mismatch of dosing. Each treatment arm will be subject to the same titration rules throughout the study, ensuring that opportunities for optimization and control of androgens are the same in both arms and thus minimizing bias in the management of participants. These androgen precursor limits have been defined based on data from previous studies in the clinical development program.

If a participant shows persistent signs of under-replacement on the randomized starting dose of 30 mg Chronocort or IRHC they will be monitored and if symptoms do not resolve the participant should be withdrawn from treatment and given alternative therapy at the Investigator's discretion. If a participant shows persistent signs of under-replacement during the titration period and the participant has received at least 1 down titration of 5 mg, a reversion to the previous dose is permitted (i.e. an increase of 5 mg) after discussion with the medical monitor. If symptoms persist, no further dose increases can be made, and the participant should be withdrawn from study treatment (such cases should be discussed with the medical monitor). If the Investigator thinks that the dose needs to be adjusted between visits, they should contact the medical monitor to discuss the case. For emergency situations, the emergency treatment pack can be used, and the medical monitor should be contacted as soon as possible.

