8.2.2. Adrenal Insufficiency Checklist

The adrenal insufficiency checklist (Appendix 5) is completed by the Investigator for all participants at Visits 1, 2, 3, 4, 5, and 6. The adrenal insufficiency checklist should only be used to determine if symptoms of under- or over-replacement of glucocorticoids have occurred since the last visit and this questionnaire should not be used to record AEs due to other causes.

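### The checklist's more-than-weekly threshold also governs syncope, so a single syncope from under-replacement does not by itself trigger the brake on a 5 mg dose reduction

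*Protocol*

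**What the plan says.** Appendix 5 of the Protocol is a form with 15 named symptoms and an Other row. One question governs every row: "Have you experienced any of the following symptoms more than once per week in the last 4 weeks". Syncope is one of the named rows and has no threshold of its own. A Yes leads to the attribution, "If Yes, do you believe this to be related to under or over replacement of glucocorticoid". A final column, not conditioned on a Yes, reads "Any clinically significant findings? Y/N"; it is not defined.

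The form's purpose is stated without any frequency condition. Its header speaks of symptoms that "have occurred in the preceding 4 weeks". Section 8.2.2, repeated in Section 4.2, says that the checklist "should only be used to determine if symptoms of under- or over-replacement of glucocorticoids have occurred since the last visit".

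The form matters because of the titration rule in Section 4.2. When 17-OHP is below 300 ng/dL and A4 is below its sex-specific limit, "then the dose will be adjusted down by a total of 5 mg". The stated exception is: "Clinical symptoms of adrenal insufficiency on the adrenal insufficiency checklist should take precedence over androgen results and would inhibit titration". Section 4.1 has the Investigator complete an "adrenal insufficiency checklist at each visit which will be made available to the independent blinded physician". Footnote 12 of the Schedule of Activities, Section 6.3 and Section 8.1.3 name the checklist and the androgen results as the basis for each decision.

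**The concern.** Section 4.2 already decides that symptoms of adrenal insufficiency outrank low androgens and stop a reduction. That rule can only act on what the form captures. A frequency filter makes sense for non-specific complaints such as headache, fatigue or poor sleep. It does not suit a sudden loss of consciousness, where one episode attributed to under-replacement is reason enough to pause a dose cut.

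What is at stake is an individual participant's safety at a titration step: the dose could go down in someone who recently had a syncope from too little glucocorticoid, because the question filtered the event out. The point does not touch the sample size, the type I error rate or the comparison between arms.

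**Working it through.** The plan gives no figure to reproduce here. The check is of wording, plus a bound on size.

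**1. Does one syncope count as a Yes?** Take k episodes in the 4-week window.
- Threshold read as an average: Yes requires k/4 > 1. For k = 1, 1/4 = 0.25, so No. For k = 4, 4/4 = 1.0, still No. For k = 5, 5/4 = 1.25, the first Yes.
- Threshold read as any one week: Yes requires at least 2 episodes in the same week, so k = 1 is No.

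A single syncope is No on either reading.

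**2. How do the texts compare?**

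| Place | What is asked | Frequency limit |
|---|---|---|
| Appendix 5, header | Symptoms occurring in the preceding 4 weeks | None |
| Sections 4.2 and 8.2.2 | Symptoms occurring since the last visit | None |
| Appendix 5, question | Symptoms in the last 4 weeks | More than weekly |

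Only the question adds a threshold. It conflicts with the purpose stated in the other places.

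**3. What follows from a No?** The attribution is skipped and the row carries no symptom. If both androgens are below their limits, the default reduction applies. The remaining ways of putting the event on the form are the undefined findings column and the Other row, which sits under the same question.

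**4. How many decisions could be touched?** About 50 participants (Section 9.2) × 3 titration visits (Weeks 4, 10 and 16) = 150 at most. An affected decision also needs androgens low enough for a reduction, a syncope attributable to under-replacement that falls short of the threshold, and no flag by another route. The documents give no frequency for any of these, so no estimate is made.

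**5. How large is a step?** 5/30 = 16.7%, 5/25 = 20% and 5/20 = 25% of the daily dose, for the three possible steps from 30 mg to 15 mg.

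**6. What could a withheld reduction do to the endpoints?** A participant who ends at 30 mg instead of 25 mg cannot be a dose responder (Section 9.1.2), and cannot be a biochemical responder if in control at baseline (Section 9.1.1). With 25 per arm, one such participant moves a crude responder proportion by at most 1/25 = 4 percentage points and a crude arm mean dose by 5/25 = 0.2 mg. If a later titration visit makes the reduction after all, the effect may disappear.

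**The case against.** The best case against the point is that the failure needs several things to go wrong together. The Investigator, not the participant alone, completes the form (Section 8.2.2), and the stated purpose invites recording any relevant symptom. The findings column is open even after a No. The Section 4.2 brake is worded around symptoms on the checklist, not Yes answers, so a syncope flagged in that column is on the form and reaches the physician. That physician decides whether to reduce. Adverse events are asked about at every visit and call (Section 8.4), concerns go to the medical monitor (Section 6.6), participants are telephoned a week after new packs arrive (Section 4.2), and a reduction can be reverted (Section 4.1). The participants exposed are also those with 17-OHP below 300 ng/dL, a quarter of the 1200 ng/dL limit for optimal control, so under-replacement is less expected in them.

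Most of this stands, and it is why the point is minor. It does not remove it. None of these routes is a stated brake on the reduction itself, and the findings column has no definition or stated link to titration. Section 4.1 sends androgen results to the blinded physician, so the Investigator has no evident prompt that a reduction is pending.

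Two stronger readings are tempting. A reader might infer that no information beyond the checklist and androgens reaches the physician. The Protocol does not say that adverse-event or medical-monitor information does, but silence is not proof. Section 2.3 describes clinical review feeding the physician's recommendations in general terms and is partly redacted, and the Amendment 1 rationale in Appendix 8 mentions detailed titration guidelines that are not among the documents. A reader might also infer that vomiting needs the same change. The default stress-dosing rules in Appendix 6 already act on vomiting, and any event that triggers stress dosing is reported as an event of special interest (Section 8.4.8). Syncope is named neither in those rules nor among the adrenal-crisis signs in Section 8.4.8.

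**Conclusion.** The point holds as a minor safety improvement. Read literally, the form gives the wrong answer for a single syncope attributable to under-replacement, and the Section 4.2 brake then depends on the Investigator's choice of another column or route. Of at most 150 checklist-informed decisions, the number affected is unknown and probably small.

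This assumes that the form is used as printed and that no training or guideline outside the documents tells Investigators to ignore the threshold for syncope.

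A reader might infer a bias between arms or a threat to the primary comparison. The documents do not support that: both arms are blinded and use the same form and titration rules. Nor do they show that any reduction was, or will be, made unsafely.

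**What to change.** In Appendix 5, change the syncope row only. Ask whether any syncope has occurred since the last visit, followed by the existing over/under attribution. Leave the other 15 rows, including vomiting, as they are. Section 4.2 needs no new text, because its rule on checklist symptoms then applies. For this row the change also covers the full six-week gap before Visits 4 and 5.

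The direct cost is rewording one of 16 rows on one form. The downside is an occasional reduction withheld. That participant stays on a higher dose, may become a non-responder under the 25 mg criteria, and slightly raises the mean dose. The same rule applies in both arms.

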Appendix 6: Stress Dosing Rules

Each site should follow their own stress dosing rules, or if these are not available then the following rules should be used:

ADRENAL INSUFFICIENCY

Your body does not make adequate cortisol or aldosterone. Cortisol is a hormone which has many purposes in the body including maintaining blood pressure. Normally cortisol is secreted in the body in small amounts every day by the adrenal glands. In addition to the usual production of cortisol, the body normally has the ability to increase cortisol production in response to various stressors such as infection or trauma. Aldosterone is a hormone which is important in regulating salt and water balance. Sufficient aldosterone is necessary to prevent dehydration. These two hormones are being replaced in your body by medications.

Extra hydrocortisone must be given during times of **extreme physical stress** such as illness with fever and significant trauma.

For illnesses which result in:

Fever greater than or equal to 100°F (37.7°C)/ minor illnesses: take 10 mg **hydrocortisone** three times a day in addition to the usual daily dose of study medication.

Fever greater than or equal to 101°F (38.3°C)/ more severe illness: take 20 mg **hydrocortisone** three times a day in addition to the usual daily dose of study medication.

Vomiting: If you vomit, wait one half-hour and then take 20 mg of hydrocortisone for stress dosing rules from your packet provided. If you vomit the study medication dose do not take another dose of study medication until the next dose is due. Call the study team to let us know you are sick. If you are vomiting and cannot keep the medication down (vomit less than 1 hour after the dose), you need to administer injectable hydrocortisone. **Do not delay giving injectable hydrocortisone.** Drink **SMALL** amounts of clear liquids frequently, as tolerated. Call your doctor or go to an emergency room if your symptoms worsen or you do not improve within one hour.

Watch for signs of acute cortisol deficiency: headache, nausea, abdominal pain, dehydration, confusion, weakness, fatigue.

An injectable form of hydrocortisone must be kept in an easily accessible location for emergencies (i.e., purse, briefcase, desk at work). It may be kept for several years in the unmixed form at room temperature. It should not be exposed to extreme hot or cold (i.e., do not store in the glove compartment of a car). Check the expiration date routinely and obtain a prescription refill when needed. Also make sure you have the needle necessary to inject the medication.

Your dose of hydrocortisone for injection is 100 mg – 2 mL by intramuscular injection to the thigh.

Other points to remember:

- When you are sick, drink sugar and salt containing liquids (e.g., non-diet soda, Gatorade, Lucozade, soup).
- If you need to have surgery, extensive dental work, or you have been in an accident, extra doses of hydrocortisone will be needed, usually by intramuscular injection or intravenous administration. Notify any physician or dentist that you have ADRENAL INSUFFICIENCY, so proper amounts of hydrocortisone can be given prior to a procedure.
- It is essential that you wear a medical identification bracelet or necklace to alert people in times of emergency that you have adrenal insufficiency and are taking medication. It is also a good idea to have a wallet card or something on your driver's licence identifying you as having ADRENAL INSUFFICIENCY.
- Call your doctor for:
Fever for more than three days
Changes in behavior, such as acting confused
- If you are living with someone, let them know to seek medical help on your behalf if you are unresponsive or difficult to arouse.

Ensure that you have a list of important phone numbers:

Nurse:

Doctor:

Pharmacy:

